#### **Example SAS Code:**

```
proc mixed data=xxx;
by parameter;
class device location strat_weight;
model log_pk = device location strat_weight / residual;
lsmeans device / alpha=0.1 cl pdiff;
ods output lsmeans=lsmeans diff=diffs;
run;
```

The  $t_{max}$  of mirikizumab between the AI (Test) and PFS (Reference) administrations will be analyzed using a Wilcoxon rank sum test. Estimates of the median difference, 90% CIs, and p-values from the Wilcoxon rank sum test will be calculated.

Additional comparisons will be made between:

- The 2 delivery devices (AI [Test] versus PFS [Reference]) separately at each injection location (injection location will be removed from the model above)

- The 3 injection locations (arm [Test] versus abdomen [Reference] and thigh [Test] versus abdomen [Reference]) separately for each device (device will be removed from the model above)

The 2 delivery devices (AI [Test] versus PFS [Reference]) will be considered bioequivalent if the 90% CI of the ratio of geometric least squares means of  $C_{max}$ , AUC (0- $\infty$ ), and AUC(0- $t_{last}$ ) fall within 0.8 to 1.25. There would not be power in the model to achieve bioequivalence boundaries for any specific injection location, therefore the bioequivalence for the 3 injection locations will not be determined.

PK parameters may be normalized by body weight for summarizing data. Additional PK analyses may be conducted if deemed appropriate.

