## 4.2. Scientific Rationale for Study Design

Conducting the study in healthy participants mitigates the potential confounding effects of the disease state and concomitant medications in participants with UC. A population of healthy participants is frequently used in the assessment of the PK of both small and large molecules.

Single doses of mirikizumab and the PK sampling time points have been selected to generate PK profiles sufficient to fulfill the study objectives.

Participants will be randomized to receive injections in the arm, thigh, or abdomen, as injection location has been observed to have an impact on bioavailability in some studies with mirikizumab.

Previous population PK analyses have shown that patients with a lower body weight tended to have a lower clearance and/or central volume of distribution. While the effects of body weight on these PK parameters were statistically significant, it was not considered to be clinically relevant. However, to mitigate these potentially confounding effects, approximately equal numbers of participants in each weight category are proposed to avoid a large difference in mean weight between the test and the reference delivery-device groups. A participant population of 72 per weight group is an approximate target with the recommended weight categories selected based on the distribution of weights in prior studies. The number of participants assigned to each delivery device and the number of participants assigned to each site of injection is desired to be balanced.

A parallel-group design is chosen because a crossover design is impractical for mirikizumab, which has a half-life of approximately 10.5 days. Additionally, a crossover study could confound PK data if participants develop neutralizing antidrug antibodies (ADAs).

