##### **9.4.2.2. Pharmacokinetic Statistical Inference**

The  $C_{max}$ , AUC(0- $\infty$ ), and AUC(0- $t_{last}$ ), will be log-transformed and analyzed using a linear fixed-effects model. The model will include delivery device, injection location, and weight stratification as fixed effects. The dosing regimen differences between AI and PFS administrations will be back-transformed to present the ratios of geometric least squares means and the corresponding 90% CI. Comparisons will be made between the 2 delivery devices and then between the 3 injection locations.

The 2 delivery devices will be considered bioequivalent if the 90% CIs of the ratio of geometric least squares means fall within 0.8 to 1.25.

The  $t_{max}$  of mirikizumab between AI and PFS administrations will be analyzed using a Wilcoxon rank sum test. Estimates of the median difference, 90% CIs, and p-values from the Wilcoxon rank sum test will be calculated.

Additional PK analyses may be conducted if deemed appropriate.

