## **5. STUDY DESIGN**

Study AMBW is a Phase 1, open-label, 2-arm, randomized, parallel-design, single-dose, multi-site study in healthy participants. At screening, participants will be stratified into 1 of 3 weight categories (less than 70 kg, 70 to 80 kg, and more than 80 kg).

Eligible participants will be admitted to the clinical research unit (CRU) on Day -1.

Within the 3 weight categories, participants will be randomized using a computer-generated allocation code:

- 1:1 to delivery device (either PFS [reference] or AI [test])
- within each delivery-device group 1:1:1 to injection site (abdomen, arm, or thigh)

On Day 1, participants will receive a  $2 \times 1$  mL (total 200 mg mirikizumab) SC dose delivered via the device and in the location assigned by the randomization.

Participants may be allowed to leave the CRU after completing the 4-hour safety assessments on Day 1, or later at the investigator's discretion, and will return for PK and immunogenicity sampling and safety assessments at predefined times up to 12 weeks postdose. Participants will be monitored for safety between outpatient visits by way of telephone assessment.

Safety and tolerability will be assessed through clinical laboratory tests, vital sign measurements, recording of AEs, physical examination, and immunogenicity.

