### **9.3.2 Pharmacokinetic Statistical Methodology**

The  $C_{max}$ , AUC (0- $\infty$ ), and AUC(0- $t_{last}$ ), will be log-transformed and analyzed using a linear fixed-effects model. The model will include delivery device, injection location, and weight stratification as fixed effects. The dosing regimen differences between AI and PFS administrations will be back-transformed to present the ratios of geometric least squares means and the corresponding 90% CI.

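### The tmax device comparison ignores injection site and weight category, so it is conservative if site shifts tmax; a stratified rank test is a free, low-priority improvement

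*SAP*

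**What the plan says.** For tmax, SAP 9.3.2 states that the parameter "of mirikizumab between the AI (Test) and PFS (Reference) administrations will be analyzed using a Wilcoxon rank sum test". Protocol 9.4.2.2 specifies the same test and adds: "Estimates of the median difference, 90% CIs, and p-values from the Wilcoxon rank sum test will be calculated". Neither document names strata, an aligned-rank method or code for tmax.

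For Cmax and the two AUCs, SAP 9.3.2 says: "The model will include delivery device, injection location, and weight stratification as fixed effects".

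The design sections (Protocol 4.1, SAP 5) randomise device 1:1 within three weight categories, and injection site 1:1:1 within each device group. Table AMBW.1 plans 12 participants per device, site and weight cell: 6 × 12 = 72 per weight category and 3 × 72 = 216 in all. Protocol 4.2 adds that "the number of participants assigned to each site of injection is desired to be balanced". It gives as the reason for varying the site that "injection location has been observed to have an impact on bioavailability in some studies with mirikizumab".

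Protocol 9.4.2.1 names tmax as the secondary PK parameter. It is not listed in the objectives and endpoints tables and is not part of the bioequivalence criterion.

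**The concern.** Balancing device across site and weight removes differences between sites and weight categories from the AI-versus-PFS contrast. An analysis that pools all 216 participants still includes those differences in its variance. If site affects tmax, the null variance of the pooled rank-sum statistic is therefore too large for this design. The test then rejects less often than its nominal level, and the matching 90% CI covers more than 90% and is wider than it needs to be.

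What is at stake is sensitivity. An autoinjector could plausibly change absorption speed, and tmax is the parameter that would show it. A conservative comparison makes a real difference easier to miss and a null result easier to over-read as similarity. The plan adjusts its primary PK parameters for these two factors and gives no reason for leaving them out for tmax.

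**Working it through.** **1. The plan's own figure.** The only stated power concerns Cmax and AUC: about 90% with 108 per group, CV 40%, ratio 1.07 and limits 0.80 to 1.25 (Protocol 9.2, SAP 7).
- SD(log) = √ln(1 + 0.40²) = 0.385, and SE = 0.385 × √(2/108) = 0.0524.
- Upper side: (ln 1.25 − ln 1.07)/0.0524 = 2.97. The lower side adds almost nothing.
- Normal approximation: Φ(2.97 − 1.645) ≈ 0.907. The exact calculation gives 0.905.

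The figure reproduces. It does not involve tmax, for which the documents state no power.

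**2. Inputs for tmax.**
- From the documents: 108 per device; nine site-by-weight cells with 12 per device in each; two-sided 10% level (90% CI); early PK samples 2, 4, 7, 10 and 14 days after dosing (Schedule of Activities, Days 3, 5, 8, 11 and 15).
- Assumed, because the documents give no tmax figures: log-normal tmax, median 5 days, within-cell log-SD 0.5, the same site pattern for both devices, and adjacent site gaps of 0.2, 0.35 or 0.5 on the log scale. The extreme site medians then differ by e^0.4 = 1.5, e^0.7 = 2.0 or e^1.0 = 2.7 times.

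**3. Approximate size by hand.** With gap g, the between-site variance is 2g²/3 and the within-cell variance is 0.25. The pooled statistic's true SD is about r = √[0.25/(0.25 + 2g²/3)] instead of 1. The size is about 2[1 − Φ(1.645/r)], and the pooled interval is about 1/r times as wide as the stratified one.

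| g | 2g²/3 | r | 1.645/r | Size | 1/r |
|---|---|---|---|---|---|
| 0.2 | 0.027 | 0.951 | 1.73 | 8.4% | 1.05 |
| 0.35 | 0.082 | 0.868 | 1.90 | 5.8% | 1.15 |
| 0.5 | 0.167 | 0.775 | 2.12 | 3.4% | 1.29 |

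**4. Simulated size and power.** This used the planned design, tie-corrected variances and a device shift of 0.15 on the log scale (e^0.15 = 1.16, a 16% shift). Where a range is given, it spans separate simulation runs. In the two lower-gap rows, the lower power comes from tmax rounded to sampling days.

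| Site spread | Size, unstratified | Power, unstratified | Power, van Elteren |
|---|---|---|---|
| 1.5-fold | about 8-9% | 63-67% | 64-67% |
| 2-fold | about 5-6% | 56-59% | 64-67% |
| 2.7-fold | about 3-4% | 47-48% | 64-67% |

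The van Elteren test stays at about 10% throughout. At g = 0.1 both tests have 66% power. With no site effect they perform alike, and stratifying costs at most about one point of power.

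**5. Simulated interval.** A separate run used continuous tmax on the log scale and Hodges-Lehmann 90% intervals.

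| Site medians | Coverage, unstratified | Width, unstratified | Width, aligned | Ratio |
|---|---|---|---|---|
| equal | 89.9% | 0.230 | 0.231 | 1.00 |
| 1 / 1.25 / 1.5 | 92.5% | 0.243 | 0.230 | 1.05 |
| 1 / 1.5 / 2 | 94.1% | 0.267 | 0.231 | 1.16 |
| 1 / 2 / 3 | 97.3% | 0.318 | 0.231 | 1.38 |

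The aligned interval covers 89.5-91.5%.

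**6. Weight alone.** An assumed ±0.15 log shift across weight categories, with no site effect, gives an unstratified size of about 9%. Site is the factor that matters.

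**The case against.** **The size is assumed.** The site effects in Protocol 2.2 and 4.2 concern exposure: up to 73% higher in thigh than abdomen with PFS, and up to 36% lower in arm than abdomen with AI. A reader might infer from these that site is known to change tmax. The documents do not support that, because extent of absorption is not time to peak. This stands, and the point is therefore conditional.

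**Mild site effects cost almost nothing.** This also stands. The loss becomes material only at about a 2-fold spread in site medians under the assumed SD.

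**Sampling times may dominate the interval.** If tmax is rounded to scheduled days, the Hodges-Lehmann interval under no device effect usually collapses to [0, 0], whether or not sites differ. This stands for heavily tied data. SAP 9.3.1 uses actual sampling times, so real data will be less tied, but some coarseness will remain under either method.

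**Device effects may differ by site.** In the earlier device bioavailability study, exposure with AI was up to 62% higher than with PFS in the abdomen. If tmax behaved similarly, one overall shift would average unlike effects. This is true, but equally so of the pooled test. The planned by-location comparisons are worded as changes to the linear model and do not clearly cover tmax.

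**Site is not strictly a stratification factor.** Only weight is. Site is a second randomised factor whose balance is desired, and block details are not given. The mechanism holds to the extent that the schedule delivers the planned cells.

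**Nothing is decided on tmax.** It has no margin, hypothesis or decision rule, and the planned test errs on the conservative side. This limits the priority but does not remove the case for a change that costs almost nothing.

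**Conclusion.** The point holds conditionally and at low priority. If injection site shifts tmax and device is balanced across sites as planned, the unstratified test runs below its 10% level and its 90% CI is too wide. Both effects are small at a 1.5-fold spread in site medians and material from about 2-fold. The direction follows from the design. The magnitudes rest on the assumed median, SD and common site pattern.

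Three stronger readings should be resisted. A reader might infer that the interval is too wide whatever the data show; with no site or weight effect it is not. A reader might infer that the test is invalid or inflates false positives; the error is in the other direction. A reader might infer that the bioequivalence claim is weakened; that claim rests on Cmax and the two AUCs, which are adjusted for both factors, and the stated 90% power reproduces.

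**What to change.** In SAP 9.3.2, specify for the overall AI-versus-PFS comparison of tmax a van Elteren (stratified Wilcoxon) test with injection location by weight category as strata. Report with it a stratified or aligned Hodges-Lehmann estimate of the device difference and its 90% CI. Keep the unstratified Wilcoxon result as a supportive analysis. Add a sentence that a non-significant tmax result is not evidence of similarity.

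Protocol 9.4 allows analysis changes that do not alter a principal feature to be described and justified in the SAP and study report. The change should therefore be recorded in SAP 11, which currently reports none. The cost is a few lines of SAP text and code, with no new data and no change to the sample size. It is best made before tmax is compared by device.

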## 2. Introduction

### 2.1. Study Rationale

Study I6T-MC-AMBW (AMBW) will assess the pharmacokinetics (PK), safety, and tolerability of a 200-mg subcutaneous (SC) dose of mirikizumab (LY3074828) solution formulation administered using an investigational manual 1-mL pre-filled syringe (PFS) or an investigational 1-mL autoinjector (AI). Both devices will be evaluated at 3 different injection sites (arm, thigh, and abdomen) in order to expand the options for administration in patient use. The study will provide data to bridge PFS administration of mirikizumab, with the investigational AI device planned for use in subsequent studies and patient use.

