### 2.2. Background

Mirikizumab is a humanized immunoglobulin G4–variant monoclonal antibody that is directed against the p19 subunit of interleukin (IL)-23 and does not bind IL-12. Mirikizumab is being developed for the treatment of autoimmune diseases, including psoriasis, Crohn’s disease (CD), and ulcerative colitis (UC), in which the IL-23 pathway is thought to have a significant pathogenic role.

Clinical pharmacology studies have demonstrated an acceptable safety profile in healthy subjects following single dose IV administration up to 2400 mg (see Section 2.2.1).

Bioavailability of mirikizumab when administered SC by either PFS or AI at different injection sites was evaluated in study I6T-MC-AMBE (AMBE). No statistically significant difference in exposure following administration with the PFS compared to the AI was noted. Comparison of AUC by injection location showed the highest AUC ratio was 1.5 for the PFS (thigh versus abdomen) and 1.4 for the AI (abdomen versus arm) (see Section 2.2.4).

Administration of a 200-mg dose via AI would improve ease of administration in patients with UC, thus there is a need to investigate the bioavailability of this dose administered by AI at various injection sites.

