### **2.2.4. Pharmacokinetics**

Studies in healthy participants and participants with psoriasis, UC, or CD found that systemic exposure of mirikizumab increases in proportion to dose, and that mirikizumab has a half-life of approximately 10 days and SC bioavailability of 40%.

Study AMBE investigated the PK, safety and tolerability of and pain associated with a 125-mg SC dose of mirikizumab solution formulation administered using the investigational manual PFS, or the investigational AI. Doses were administered as 1× 1-mL SC injections into the arm, thigh, or abdomen. When all injection sites were considered together, the study showed no statistically

significant difference in exposure following administration with the PFS compared to the AI; however, the upper bounds of the 90% CI for AUC(0-tlast), AUC(0-∞), and Cmax were greater than the 1.25 bioequivalence boundary. Comparison of exposure by injection location demonstrated statistically significant differences (that is the 90% CI for the ratio of geometric least squares means excluded unity) when comparing the 2 administration methods:

- PFS and AI administration into the abdomen
  - exposure increased by up to 62% following administration using the AI compared to PFS

And for each administration method the following statistically significant differences were noted between injection sites:

- AI administration into the arm compared to the abdomen,
  - exposure decreased by up to 36% following administration into the arm compared to the abdomen
- PFS administration into the thigh compared to the abdomen.
  - exposure increased by up to 73% following administration into the thigh compared to the abdomen.

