### 3. Objectives and Endpoints

Objectives	Endpoints
Primary	

 
To evaluate the PK of mirikizumab after SC administration of 200-mg doses of solution formulation using a 2× 1-mL PFS and a 2× 1-mL AI in healthy participants
 
	
 
<math>C_{max}</math>, <math>AUC(0-\infty)</math>, and <math>AUC(0-t_{last})</math>
 

Secondary	

 
To describe the safety and tolerability of mirikizumab in healthy participants
 
	
 
TEAEs and SAEs
 

Tertiary/Exploratory	

 
To evaluate the effect of mirikizumab delivery device on immunogenicity
 
To evaluate the impact of injection-site location on PK
 
	
 
TE-ADA
 
<math>C_{max}</math>, <math>AUC(0-\infty)</math>, and <math>AUC(0-t_{last})</math>
 

Abbreviations: AI = autoinjector;  $AUC(0-\infty)$  = area under the concentration versus time curve from time zero to infinity;  $AUC(0-t_{last})$  = area under the concentration versus time curve from time zero to time  $t$ , where  $t$  is the last time point with a measurable concentration;  $C_{max}$  = maximum observed drug concentration; PFS = pre-filled syringe; PK = pharmacokinetics; SAE = serious adverse event; SC = subcutaneous; TE-ADA = treatment-emergent antidrug antibody; TEAE = treatment-emergent adverse event.

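### Does the bioequivalence analysis need a formal device-by-injection-site comparison to be sound?

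*SAP*

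**What the plan says.** SAP 9.3.2 specifies the primary analysis of log-transformed Cmax, AUC(0-∞) and AUC(0-tlast): "The model will include delivery device, injection location, and weight stratification as fixed effects". Protocol 9.4.2.2 names the same terms. The example code takes one device contrast from that model, and the 0.8 to 1.25 rule is applied to its 90% CI for all three parameters.

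Two sets of supporting comparisons follow in the SAP. The first is AI versus PFS "separately at each injection location (injection location will be removed from the model above"). The second compares arm and thigh with abdomen, separately for each device. Together they elaborate the protocol's line: "Comparisons will be made between the 2 delivery devices and then between the 3 injection locations". The SAP adds that power is lacking at any specific site, "therefore the bioequivalence for the 3 injection locations will not be determined".

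On purpose, Protocol 2.1 says: "The study will provide data to bridge PFS administration of mirikizumab". It also wants to widen the choice of injection sites. Protocol 3 lists site among the exploratory objectives: "To evaluate the impact of injection-site location on PK".

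**The concern.** Neither document plans a device-by-location term, a ratio of the site-specific AI/PFS ratios with a CI, or a test of whether those ratios differ. Nor does any sentence say in words that a bioequivalence conclusion is an average over sites.

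The sponsor's own background makes the question reasonable. In AMBE, Protocol 2.2 reports that "the highest AUC ratio was 1.5 for the PFS (thigh versus abdomen) and 1.4 for the AI (abdomen versus arm"). If that means the largest of all pairwise site contrasts, the abdomen had the lowest AUC with PFS and the highest with AI. The abdominal AI/PFS ratio was then at least 1.5 times the thigh's and 1.4 times the arm's. Protocol 2.2.4 adds that abdominal exposure was up to 62% higher with AI, and that the pooled upper 90% bounds "were greater than the 1.25 bioequivalence boundary".

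If the additive model were wrong under such a pattern, or if a pooled pass could be read as a pass at every site, the bridge from PFS to AI would be weaker than it appears.

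**Working it through.** **Inputs.** From SAP 7: 108 per device, CV 40%, expected ratio 1.07, limits 0.8 to 1.25, 90% CI. From SAP 5: 1:1:1 allocation to site within device, so 216/6 = 36 completers per device-by-site cell. Log-scale variance σ² = ln(1 + 0.40²) = 0.1484, so σ = 0.3853. All results are for one PK parameter; the rule needs all three, so the joint chance of passing is no higher.

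**1. The plan's own figure.** Two one-sided 5% t-tests with 108 per group give power 90.5%, against about 90% stated. The 90% CI factor for the device ratio is exp(1.652 × 0.3853 × √(2/108)) = 1.09.

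**2. What the additive model estimates.** With equal cells, the device contrast is the simple average of the three site log-ratios, whether or not they differ. An omitted interaction leaves that estimate unchanged and goes into the residual. With λ = 18 × Σ(site log-ratio − mean)² / σ² and 210 residual df, the CI is wider on the log scale by √((210 + λ)/210).

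Scaling the AMBE pattern to an overall ratio of 1.07 gives abdomen 1.370, arm 1.370/1.4 = 0.979 and thigh 1.370/1.5 = 0.913.
- Log-ratios 0.3148, −0.0212 and −0.0910; mean 0.0675.
- Squared deviations sum to 0.0942, so λ = 18 × 0.0942/0.1484 = 11.4.
- CI widening √(221.4/210) = 1.027, or 2.7%.
- Probability of passing 89.8%, against 90.5% with equal site ratios.

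The effect is small and on the cautious side.

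**3. Whether a pooled pass hides a site excess.** That 89.8% depends on holding the overall ratio at 1.07, which forces arm and thigh below 1. Other patterns (the site ratios are assumptions, except the 1.62 from AMBE):

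| Abdomen / arm / thigh | Overall ratio | Probability of passing |
|---|---|---|
| 1.37 / 0.98 / 0.91 | 1.07 | 90% |
| 1.37 / 1.00 / 1.00 | 1.11 | 72% |
| 1.37 / 1.07 / 1.07 | 1.16 | 39% |
| 1.62 / 1.00 / 1.00 | 1.17 | 30% |
| 1.62 / 1.16 / 1.08 | 1.27 | 3% |

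A large abdominal excess that the other sites do not offset often fails the planned rule. One that they do offset passes, correctly, because the average is then within limits.

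**4. Whether the site comparison is lost.** Each AI/PFS site fit uses different participants, so the log-ratios are independent and their difference is the interaction contrast. In a balanced simulated data set, the difference between two site-fit estimates equalled the interaction coefficient (0.0748 both ways).
- From the interaction model (208 df): CI factor exp(1.652 × 0.3853 × √(4/36)) = 1.236.
- From two planned site fits, each with 72 − 4 = 68 df and factor exp(1.668 × 0.3853 × √(2/36)) = 1.163: combined factor exp(√2 × ln 1.163) = 1.24.

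The two routes give the same estimate and practically the same precision. The site comparisons within each device offer a second route.

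**5. The SAP's statement on site-level power.** With 36 per device at one site, power for bioequivalence is 46% at a true ratio of 1.07 and 57% at 1.00. Declining to determine bioequivalence by site is justified.

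**The case for a change.** The best argument for the extra model is that passing the rule says little about spread between sites: 90% for both equal ratios and 1.37 / 0.98 / 0.91. An interaction estimate would be informative about large differences. The 2-df test at 10% has 92% power for that pattern and 75% for an abdominal ratio of 1.30 with the other two sites equal and the overall ratio 1.07. Stating it in advance would fix the contrasts and CI level before the data are seen, at the cost of a few lines. The table shells are not available, and SAP 9.1 limits statistical analysis to what the SAP details, so they cannot be assumed to fill the gap.

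The facts stand: no such comparison is pre-stated, and the word average does not appear. They do not amount to a defect. The stated objectives ask about the device and about the effect of location on PK; none asks whether the device ratio varies by site. The reported site ratios already let a reader see and quantify any spread. The test would have only 38% power at an abdominal ratio of 1.20, with a 10% false-flag rate per parameter. The AMBE signal rests on one reading of a sentence and on a single 125-mg injection. Its sample size and its arm and thigh device ratios are not given.

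**Conclusion.** The concern does not hold. Followed as written, the plan gives a valid decision on the average AI/PFS ratio with the stated power of about 90%. Differences between sites cost little: under the AMBE-like pattern, a CI 2.7% too wide and a pass probability of 89.8% instead of 90.5%. The site-specific ratios will be reported, and their differences can be recovered with a 90% CI of about ×/÷ 1.24. That the conclusion is averaged over sites follows from taking one device contrast in a model with location as a main effect, and from the explicit refusal to determine bioequivalence by site. A supportive interaction model is a matter of preference; adding or omitting it changes no planned estimate or decision.

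This rests on CV 40%, near-equal cells of 36 among completers, and per-parameter calculations. At CV 30% or 50% the factor 1.24 becomes 1.18 or 1.30, which does not alter the conclusion.

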#### **9.4.1. General Considerations**

Additional exploratory analyses of the data will be conducted as deemed appropriate. Study results may be pooled with the results of other studies for population PK analysis purposes to avoid issues with post hoc analyses and incomplete disclosures of analyses.

No adjustments for multiple comparisons will be made.

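### Should the SAP list arm versus thigh, and a location contrast from the main model, among its injection-site comparisons?

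*SAP*

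**What the plan says.** Protocol section 3 makes the site question exploratory: "To evaluate the impact of injection-site location on PK", with Cmax and the two AUCs as endpoints. Protocol 9.4.2.2 describes one additive model (device, location, weight stratum) and adds: "Comparisons will be made between the 2 delivery devices and then between the 3 injection locations". It does not say which pairs, or whether they are taken within a device or over both. Protocol 9.4 leaves the more technical description of the analyses to the SAP.

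SAP 9.3.2 fits the same main model. Its example code asks for device means only: "lsmeans device / alpha=0.1 cl pdiff". It then lists additional comparisons. One is AI versus PFS at each location. The other is "The 3 injection locations (arm [Test] versus abdomen [Reference] and thigh [Test] versus abdomen [Reference]) separately for each device", from a model without the device term. On bioequivalence by site, the SAP says that power would be lacking, "therefore the bioequivalence for the 3 injection locations will not be determined". SAP section 11 declares no changes from the protocol's analyses.

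Neither document names arm versus thigh. SAP section 3 refers to a separate document of table, figure and listing shells, which is not available here, so an output planned only there cannot be checked.

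**The concern.** A reader who sets the two documents side by side expects three site comparisons and finds two. The study randomises to site because location affected bioavailability in earlier work (Protocol 4.2), and one stated aim is to widen the choice of administration sites (Protocol 2.1). An interval for arm versus thigh therefore seems a natural output. If it were added only after the data were seen, in an open-label study, it could look selective.

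The main model also contains location and uses all participants, so it could give a tighter site contrast than the per-device fits, yet none is requested. At stake would be the completeness and precision of the site description, and the accuracy of the statement that nothing changed from the protocol.

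**Working it through.** **The plan's own figure.** Inputs from Protocol 9.2 and SAP section 7: CV 40%, expected ratio 1.07, limits 0.8 to 1.25, 90% CI, 108 per group.

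- Log-scale SD = sqrt(ln(1 + 0.40²)) = 0.3853.
- Power by two one-sided tests, integrated over the variance estimate: 90.5%, against about 90% stated. The normal approximation needs 106 per group for 90% power, against 108 planned.
- Enrolment: 216/(1 − 0.10) = 240, as stated.

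The primary comparison reproduces and does not depend on which site contrasts are listed.

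**Precision of a listed site contrast.** With 216 completers in balanced cells there are 216/6 = 36 per device and site. The per-device model has 108 − 1 − 2 − 2 = 103 residual degrees of freedom.

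- SE = 0.3853 × sqrt(2/36) = 0.0908.
- 90% CI factor = exp(t × SE), with t the 95th percentile on 103 df. This gives 1.163, so the interval is the ratio × 0.860 to × 1.163.

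**Precision of the unlisted pair.** On the log scale, arm − thigh = (arm − abdomen) − (thigh − abdomen), so the point ratio is the quotient of the two listed ratios. The listed contrasts share the abdomen mean, so their covariance is 0.3853²/36 = 0.00412, and each has variance 0.00825. Then

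var(arm − thigh) = 0.00825 + 0.00825 − 2 × 0.00412 = 0.00825 (allowing for rounding),

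which is again SE 0.0908 and factor 1.163. With balanced cells, the missing interval has the same planned width as the two listed ones and a centre that follows from them.

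| Assumption | Per-device 90% CI factor |
|---|---|
| CV 30%, 36 per site | 1.122 |
| CV 40%, 36 per site | 1.163 |
| CV 50%, 36 per site | 1.203 |
| CV 40%, 30 per site (180 evaluable, assumed) | 1.180 |

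The example code's option for pairwise differences, applied to location in a per-device fit, prints all three pairs.

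**The main-model contrast.** Here there are 72 per site and 216 − 1 − 1 − 2 − 2 = 210 df.

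- SE = 0.3853 × sqrt(2/72) = 0.0642, factor 1.112.
- On the log scale the interval is about 30% narrower (ratio of half-widths 0.704).

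The gain is for a different quantity, the site effect averaged over devices. Protocol 2.2.4 reports on the earlier study: "And for each administration method the following statistically significant differences were noted between injection sites". With the AI, exposure from the arm was up to 36% lower than from the abdomen. With the PFS, exposure from the thigh was up to 73% higher than from the abdomen. Abdominal exposure itself was up to 62% higher with the AI than with the PFS. The main model has no device-by-location term, so its location contrast would blend such effects.

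**Cost of adding both.** Protocol 9.4.1 states: "No adjustments for multiple comparisons will be made". Listed location CIs now number 2 pairs × 2 devices × 3 parameters = 12. Adding arm versus thigh gives 3 × 2 × 3 = 18, and adding the main-model contrasts gives 18 + 3 × 3 = 27. With no site differences at all, the expected number of 90% CIs excluding 1 rises from 1.2 to 1.8 to 2.7.

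**The case for a change.** The best case for a change starts from the earlier study. Protocol 2.2 gives the highest AUC ratio as 1.5 for thigh over abdomen with the PFS and 1.4 for abdomen over arm with the AI. If highest means the largest of the three pairwise ratios, thigh ranks top with the PFS and arm ranks bottom with the AI. Thigh would then be at or above arm with both devices, and the pair with the steadiest direction would be the one left out. The clause allowing further PK analyses permits the contrast but does not prespecify it.

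The literal omission stands, and permission is indeed not prespecification. The ordering argument carries little weight:

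- It rests on AUC point estimates from one study of a single 125-mg injection, without their sampling error, and on one reading of a word.
- It says nothing about Cmax, which is also a location endpoint. The exposure figures in Protocol 2.2.4 correspond to ratios of up to 1/(1 − 0.36) = 1.56 and up to 1.73. Both exceed the AUC ratios in section 2.2, so at least one exposure measure behaved differently, and its site order is not given.
- The between-site differences reported there as significant are arm versus abdomen (AI) and thigh versus abdomen (PFS). Arm versus thigh is not among them for either device. The SAP listed the two pairs that had prior evidence.

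The concern about selective reporting is also weak, because no claim or decision hangs on any location interval.

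**Conclusion.** The observation is accurate, but no change to the plan follows. Choosing abdomen as common reference and fitting each device separately is the kind of detail that the protocol leaves to the SAP. It contradicts nothing in Protocol 9.4.2.2, so the declaration of no changes is not made wrong by it. Followed as written, the SAP gives sound per-device site results for an exploratory objective with no decision rule. Only the interval for arm versus thigh is unlisted. Its centre follows from the listed ratios, its planned 90% factor is the same 1.163, and routine code would print it. An analyst may report it descriptively without any amendment. Leaving out a device-averaged contrast is a fair trade-off: the factor of 1.112 buys precision for a quantity that is harder to interpret when site effects differ by device.

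The figures assume 216 evaluable participants in balanced cells and a CV of 40%. Across CVs of 30% to 50%, and with 180 evaluable at 40%, the per-device factor stays between 1.122 and 1.203. The primary comparison, its power of about 90% and its decision rule are unaffected in every case.
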